**Good Clinical Practices**

This study was conducted under Good Clinical Practices, in accordance with the Declaration of Helsinki, in compliance with the International Conference on Harmonisation (ICH) guidelines.

### Abstract/Brief Overview:

Each year over 1,200 Fontan operations are performed on children in the United States with a congenital heart defect resulting in single ventricle physiology. This translates to over 2,500 Fontan operations annually world-wide and thousands more infants born with one functional ventricle who don't reach Fontan physiology. Fontan physiology describes a circulation where the only ventricle pumps blood to the body and blood flow to the lungs is passive, down a pressure gradient, without a pumping ventricle. Unfortunately, there can be significant long-term morbidity associated with the Fontan physiology, largely related to chronic venous congestion and difficulty traversing the pulmonary vasculature without a ventricle to power it. Nitrate based medications such as isosorbide dinitrate (ISDN) have been used in adults with heart failure demonstrating improved survival, ejection fraction, and exercise tolerance in select populations. In pediatric patients, they have recently been shown to increase venous capacitance, thereby decreasing central venous pressure within the Fontan circulation. Central venous pressure is a critical indicator of Fontan function and an instigator of morbidities in these patients. We will investigate the safety and preliminary efficacy of ISDN therapy to reduce venous congestion and improve exercise tolerance in children and adults after the Fontan operation. This will be accomplished by recruiting 15 Fontan physiology patients from the Cincinnati Children's Fontan clinic and University of Kentucky Pediatric Cardiology clinic for the investigation. We will non-invasively measure both central venous pressures at rest and during graded cardiopulmonary exercise testing. In addition we will obtain a measurement of liver stiffness before and after a 4-week regimen of ISDN therapy. Patients will be seen twice in clinic, once before and after ISDN therapy, and phone calls will be made to ensure safety, compliance, and make appropriate alterations to medications throughout the study period. Pre- and post-intervention central venous pressure and exercise tolerance will be compared.

In this investigation we hypothesize the following:

- Isosorbide dinitrate will lower central venous pressure
- The better hemodynamics associated with central vasodilation will result in greater exercise endurance and improved liver stiffness

### Purpose of Study:

[figure not shown]
This study is meant to evaluate the safety and efficacy of isosorbide dinitrate in children and adults with Fontan physiology in decreasing liver stiffness and lowering exercise related venous pressure responses and increasing exercise tolerance.

### Background:

Approximately 740 infants of every million live births are born with congenital heart disease complicated by single ventricle physiology; this translates to over 1,000 new patients undergoing the Fontan operation every year in the United States and likely between 50,000 to 70,000 patients worldwide

currently living with Fontan physiology who will go on to develop early heart failure(1,2). Furthermore, this number is expected to double in the next 20 years putting a huge burden on heart-failure and cardiac transplantation services(3). The current approach to managing patients born with one functional ventricle is a series of interventions that lead up to the Fontan operation(4,5). Prior to this surgery, patients died in infancy, but now this growing cohort of patients is surviving childhood only to develop heart failure, venous thromboses, venous hypertension, arrhythmias, plastic bronchitis, cirrhosis, and protein losing enteropathy. Unfortunately, patients with a failing Fontan circulation are the fastest growing cohort presenting to congenital heart programs with heart failure and the risk of heart failure 5-years after Fontan operation rises steeply, accounting for a large proportion of death in these patients(3). Though survival has improved, morbidity is also high, resulting in only a 60% employment rate and survival beyond young adulthood being a challenge(6).

Therefore, attention now must shift to the post-operative period, focusing on how to improve quality of life and prevent heart failure subsequent to the Fontan operation. While the Fontan circulation can fail for a number of reasons, venous congestion and elevated right-sided pressures (i.e., central venous pressure, pulmonary vascular resistance) contribute to some degree in nearly all cases. This congestion is primarily the result of having no sub-pulmonic ventricle and a diseased pulmonary vascular bed which are inherent to the Fontan circulation (Figure 1a)(7). Though ventricular assist devices have been utilized to support these patients, results are inconsistent and depend greatly on the cause of heart failure(8).

[figure not shown]
**Figure 1:** Primary hemodynamic effects of venous congestion manifested in Fontan circulation (a). Anticipated impact of oral isosorbide dinitrate therapy (b). CVP, central venous pressure; MAP, mean arterial pressure; MPAP, mean pulmonary arterial pressure; PVR, pulmonary venous resistance

Isosorbide dinitrate, which is metabolized to generate nitric oxide, has long been studied and used in adults with heart failure(9). It is suggested to improve symptoms by the American College of Cardiology

and the American Heart Association guidelines(9). It acts to dilate both the central venous and systemic arterial vasculature with minimal effect on pulmonary arteries(10). The V-HeFT II study demonstrated an improvement in ejection fraction and exercise tolerance in patients treated with hydralazine-ISDN. Unfortunately, many studies of ISDN include hydralazine (or other afterload reducers) in the regimen, which make the effect of the individual drugs difficult to assess. Recently, ISDN therapy immediately following Fontan operation and continued for one year after demonstrated a reduction in central venous pressure (CVP) compared to patients not receiving ISDN treatment(11). ISDN has a promising mechanism and background making it a potential medication to improve outcomes after the Fontan operation. Therefore, the purpose of this trial is to evaluate whether ISDN is safe in Fontan patients while improving exercise tolerance as well as reduced liver stiffness and venous pressure in response to exercise.

Maintaining a low central venous pressure is of critical importance in patients with Fontan physiology. This has typically been addressed by targeting the pulmonary vascular resistance; however, increasing the systemic venous capacitance (venous pool) by using venodilators has also been shown to decrease central venous pressure(12). The typically elevated central venous pressure seen in Fontan circulation is the result of decreased venous capacitance as a maladaptive response to preserve pre-load and thus cardiac output. While this is effective short-term, like many of our body's natural responses to heart failure, it is unsustainable and can be prevented with targeted therapy(13). Long-term Fontan physiology often met with rising pulmonary and central venous pressures leading to venous congestion with detrimental impact on end-organ function, particularly the liver. Nitrate medications, such as ISDN, are effective at increasing the systemic venous capacitance, especially of the splanchnic system, and hence lowering Fontan patient's central venous pressure with the anticipated effects as depicted in Figure 1(10). At the same time, cardiac output is maintained which could lead to decreased liver congestion and improved exercise tolerance. Ultimately, the goal of this intervention is to prevent or delay long-term failure of the Fontan circulation and counteract some of the body's maladaptive responses to the Fontan circulation.

Peripheral venous pressure has been validated in Fontan physiology to correlate with central venous pressure ( $R=0.86, p<0.0001$ ) through the equation  $CVP = 1.6 + 0.68 \times PVP$  regardless of venous collaterals or fenestration. Mean capillary filling pressure ( $P_{mcf}$ ) as another means by which to assess

**Figure 2:** From Masutani et al. "Assessment of Central Venous Physiology of Fontan Circulation Using Peripheral Venous Pressure." JCTVS. April 2017

venous compliance of a patient.  $P_{mcf}$  correlates with the PVP after rapid occlusion of arm circulation ( $P_{arm-occ}$ ) with a high-pressured cuff ( $R=0.88, p<0.0001$ ) through the equation  $P_{mcf} = 9.1 + 0.63 \times P_{arm-occ}$ .(14) See figure 2. In a more compliant vasculature,  $P_{mcf}$  would be lower for a constant blood volume. All measurements of cardiac output, central venous pressure, and mean capillary filling pressure can be measured non-invasively in the clinic. Cardiac output and venous pressures will be obtained prior to starting an exercise tolerance test and will be measured and recorded at several points throughout the test, including maximal effort. Cardiac output would be calculated non-invasively by using the inert gas rebreathing (IGR) method.(15)

Though ISDN is generally a safe medication and is frequently used in adult heart failure patients and already being used in Fontan patients at various centers, there are several concerns which must be further evaluated in pediatric Fontan patients(16). Medication tolerance is known to occur with nitrate therapy in adults; however, this effect was not seen in children undergoing ISDN therapy for one year following the Fontan operation(11,17). Also, the impact of potentially combining ISDN with phosphodiesterase inhibitors (a common medication in Fontan patients) could increase the risk for extreme hypotension and will be a contraindication to study participation. Lastly, there is the theoretical concern that decreasing pre-load could diminish cardiac filling and thereby cardiac output, especially when exercising, but this effect is likely balanced by afterload decreasing effects of ISDN acting upon other parts of the vasculature. These concerns will all be key points of the investigation into a new use of ISDN in Fontan circulations. It should be noted that our own Fontan clinic currently has multiple pediatric patients on ISDN therapy with no ill effect.

While Fontan patients are a growing population, at individual centers they still represent a very small proportion of the patients with congenital heart defects. Furthermore, they are a group of very high interest for reasons already described and existing patients are saturated with clinical trials. Therefore, obtaining large numbers of patients for long studies remains challenging in this group of patients at high risk for heart failure. Nonetheless, if shown to be an effective means of improving exercise tolerance and improving hemodynamics at a large single center Fontan clinic, this would likely warrant consideration of a randomized prospective multi-center trial which could significantly alter treatment regimens in Fontan patients.

### **Primary Objective**

**Determine the safety of a 4-week regimen of isosorbide dinitrate therapy titrated to maximal tolerated dose or 30mg and obtain estimates of the effect and variability on maximal exercise capacity in asymptomatic Fontan patients.**

### **Secondary Objectives**

**1. Determine the effect of ISDN on the hemodynamic profile including non-invasively measured central venous pressure at rest and during exercise and liver stiffness.**

- Central venous pressure as calculated from peripheral venous pressure at rest and exercising
- Cardiac output measured by IGR at rest and exercising
- Venous compliance
- Heart rate
- Systemic blood pressure
- Liver stiffness measured by ultrasound

**2. To ensure low rate of side-effects in polypharmacy of Fontan patients**

### **Study Design:**

This will be a single arm, two-center prospective clinical trial of ISDN (up to 30 mg, 3 times daily) in pediatric and adult patients greater than 9 years old who have undergone the Fontan operation and do not have Fontan failure. The dose selected was based on current treatment protocols at the Cincinnati

Fontan clinic, literature review, and discussion with adult heart failure specialists. Fifteen patients will be enrolled from our Cincinnati Children's Fontan Clinic and collaborating pediatric cardiology clinic at the University of Kentucky. We will test the hypothesis that ISDN administration over 1-month period will be safely tolerated and improve exercise venous pressure responses, as well as exercise tolerance in Fontan patients. Our primary end point will be the change in exercise tolerance after 1 month of ISDN therapy. Secondary end points will include change in central venous pressure and cardiac output at rest and during exercise, mean capillary filling pressure, systemic blood pressure, heart rate, evidence of medication tolerance, and incidence of medication side effects including headaches.

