#### **Exclusion criteria:**

- Pregnant or nursing
- Prior hospitalization for heart failure in past year
- Presence of uncontrolled arrhythmias within the past 6 months
- Non-cardiac conditions which significantly limited exercise
- Moderate or severe ventricular dysfunction by echocardiogram or cardiac MRI
- Currently treated with a phosphodiesterase-5 inhibitor or organic nitrates
- Concurrent enrollment in other investigational drug trial
- End stage Liver Disease (ESLD)

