#### *Pharmacologic Interventions*

At the conclusion of the first visit ISDN therapy will begin at a small dose (5 mg three times daily in those targeting 20-30 mg TID, less in patients < 40 kg) and be titrated up to goal three times daily over 2 weeks (see Table 2). The medication will be continued for 4 weeks once the target dose is reached. It is an organic nitrate commonly used to prevent angina and used frequently in heart failure as well. It acts upon vascular smooth muscles to cause vasodilation of the peripheral arteries and veins. It should be taken by mouth three times per day with water. It may be taken with or without food.

Patients not tolerating the medication will be instructed to call the clinic for adjustment of medications. Severe side effects to note include pre-syncope, syncope, and severe headache. The PI will assess the patient over the phone and ask them to come in if necessary. Conversation and any changes of

medications will be documented. Less severe symptoms such as mild lightheadedness or headache should attempt to be tolerated or treated with acetaminophen prior to calling the clinic.

Isosorbide dinitrate's clinically relevant interaction is with phosphodiesterase-5 inhibitors, a common medication in Fontan patients. There is a risk for excessive hypotension and therefore, will be a contraindication to enrollment in the trial. ISDN can also affect kidney function. For this reason, a basic metabolic panel will be taken at the start of the study and 1 week after initiation of ISDN.

Side effects will attempt to be reduced by a step-wise up-titration plan, use of acetaminophen for headache, and recommendation to return to previous dose if necessary which may enhance tolerability. Furthermore, patients will be followed up with by phone call 3-5 days after any change in medication.

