#### **Statistical Analyses**

Demographic and clinical characteristics of the patient population will be summarized using means and standard deviations or medians and interquartile ranges for continuous variables and frequencies and percents. for categorical variables.

The exercise endurance VO2 and all other study endpoints will be compared between the first and final visits.

Means and standard deviations will be calculated for exercise endurance at baseline and after one month of treatment. The 95% confidence intervals (CIs) for both the mean change and standard deviations will be calculated to obtain estimates of the population values under sampling variability. These values will provide us with a range of plausible values required to inform a rigorous sample size determination for a larger, confirmatory trial of isosorbide dinitrate on exercise capacity assuming no change under placebo. The mean change in VO2 divided the standard deviation will provide a measure of the standardized effect size. We expect a standardized mean difference of at least 0.2 standard deviation units in favor of the investigational agent would reflect a meaningful effect size to help support an encouraging (versus no effect) decision to proceed with a larger, confirmatory trial. We will also formally test whether the change in VO2 in response to isosorbide dinitrate is non-zero using a one-sample t-test or non-parametric alternative. This testing will be conducted using a one-sided alpha of 0.25 since our primary goal is to assess whether there may be preliminary evidence for efficacy and we are willing to accept greater risk of a type I error at this early stage of investigation.

Safety analyses will be conducted by reporting the counts of adverse events (AEs) and serious adverse events (SAEs). Lab values required to monitor patient safety will be determined by the investigators and DSMB. These values will be monitored and values reported to the DSMB over the course of the trial.

Estimates of preliminary efficacy and variability for secondary outcomes will be conducted using the approach described above for the primary outcome.

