### **Sample Size Calculation**

Null hypothesis testing is not directly related to achieving the proposed aims. Rather, our goal is obtain sufficiently precise estimates of the parameters needed to inform the design of a confirmatory trial. Based on our experience with this patient population we expect the mean exercise capacity VO2 at follow-up to be around 25 with a standard deviation of approximately 7. We would like to estimate the mean VO2 with a margin of error of not greater than four. A sample size of  $n = 15$  produces a two-sided 95% confidence interval with a distance from the mean to the limits that is equal to 3.9 when the estimated standard deviation is 7. Thus, we will enroll a total of  $n=15$  patients into this pilot study. A sample size of  $n = 15$  produces a two-sided 95% confidence interval with a width equal to 5.9 for the population standard deviation when the sample standard deviation is 7. Thus, we expect  $n= 15$  participants will allow us to obtain estimates of variability with sufficient precision to inform the design of a future confirmatory trial.

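### Secondary objective 2 sets out to ensure a low side-effect rate in polypharmacy, but counts of adverse events in 15 patients give no patient-level rate, and 15 patients can only estimate one

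*Combined protocol and SAP*

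**What the plan says.** All references are to the combined protocol and SAP.

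- **Secondary Objectives, item 2** (printed just above Study Design): "To ensure low rate of side-effects in polypharmacy of Fontan patients". No section gives a threshold for a low rate or says what counts as polypharmacy. The inclusion criteria ask for a regimen stable for 3 months, not for any number or class of drugs.
- **Exclusion criteria**: "Currently treated with a phosphodiesterase-5 inhibitor or organic nitrates".
- **Pharmacologic Interventions**: "Isosorbide dinitrate's clinically relevant interaction is with phosphodiesterase-5 inhibitors, a common medication in Fontan patients". The same section says that changes of medication made after a call will be documented.
- **Statistical Analyses**: "Safety analyses will be conducted by reporting the counts of adverse events (AEs) and serious adverse events (SAEs"). Secondary outcomes are to follow the approach used for the primary outcome.
- **Study Design** names the incidence of side effects, including headaches, as a secondary end point. The list under **Study Endpoints** omits it.
- **Sample Size Calculation**: "Thus, we will enroll a total of $n=15$ patients into this pilot study". The number rests on the precision of VO2; no side-effect rate enters it.

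**The concern.** The objective is worded as a guarantee about a rate, and the analysis does not produce a rate. A count of events does not say how many patients were affected, has no stated uncertainty, and is not set against background medication. The approach borrowed from the primary outcome (mean change, standard deviation, one-sample t-test) does not suit the incidence of a side effect.

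Safety is also part of the primary objective, so readers will look to this result. A small count could be taken as meeting objective 2 while being compatible with roughly one patient in five being affected, or more. It would also be silent on patients taking a drug that the protocol itself calls common in this population.

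**Working it through.** **Inputs.** n = 15, single arm (Study Design; Sample Size Calculation). SD 7 for VO2 (Sample Size Calculation). The plan uses 95% intervals for VO2 and states no confidence level for adverse-event rates, so both the two-sided and one-sided 95% limits are shown. Assumption: all 15 patients take the drug and contribute safety data.

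**1. The plan's own figures.**
- Half-width for the mean: t(0.975, 14) × 7/√15 = 2.145 × 1.807 = 3.88. The plan gives "distance from the mean to the limits that is equal to 3.9 when the estimated standard deviation is 7". It reproduces.
- Interval for the SD: 7 × √(14/χ²), with the 97.5% and 2.5% chi-square quantiles on 14 degrees of freedom, gives 5.12 to 11.04, a width of 5.91 before rounding. The plan gives "width equal to 5.9 for the population standard deviation when the sample standard deviation is 7". It reproduces.

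The sample size is therefore internally sound for VO2. Neither figure bears on a side-effect proportion.

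**2. What 15 patients can say about a proportion.** The exact (Clopper-Pearson) upper limit for x affected of n is the 0.975 quantile (two-sided) or 0.95 quantile (one-sided) of Beta(x+1, n−x). For x = 0 it reduces to 1 − 0.025^(1/15) or 1 − 0.05^(1/15).

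| Patients affected | Two-sided 95% upper limit | One-sided 95% upper limit |
|---|---|---|
| 0/15 | 21.8% | 18.1% |
| 1/15 | 31.9% | 27.9% |
| 2/15 | 40.5% | 36.3% |
| 3/15 | 48.1% | 44.0% |

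The rule of three gives 3/15 = 20.0% for zero events, in line with the first row.

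**3. Chance of seeing nothing.** A side effect with a true rate of 10% is missed entirely with probability 0.90^15 = 0.206. One with a true rate of 5% is missed with probability 0.95^15 = 0.463.

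**4. Why event counts do not replace a rate.** As an illustration, three recorded headaches could come from one patient (1/15 = 6.7%, upper limit 31.9%) or from three patients (3/15 = 20%, upper limit 48.1%). A count of three does not tell these apart.

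**5. Background drugs.** Medication review is scheduled at Visit 1 only (Baseline visit; Table 1). Proposed Dose allows background drugs to be adjusted when a patient has symptoms, so the Visit 1 list may not describe what the patient was taking when an event occurred. The changes are to be documented, but no analysis uses them. The Relationship section classifies each event against the study drug only. The documents give no distribution of background drugs, so no limits by drug group can be computed.

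**The case against.** The best defence is that *ensure* is meant operationally. The protocol has step-wise titration, acetaminophen for headache, return to the previous dose, adjustment of background drugs, and a DSMB whose review is required before enrolment resumes after a serious event. On that reading the objective describes care taken, not an inference. This is plausible, but the item stands among the study objectives, Study Design names side-effect incidence as an end point, and an end point needs an analysis.

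It is also fair to say that wide limits are a property of any 15-patient pilot, that the plan disclaims hypothesis testing as its aim, and that zero events is unlikely because the risk section calls nitrate headache common. All of this stands. It argues for wording the objective as estimation; it is not a case for more patients.

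Three stronger readings are tempting, and the documents do not support them:

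- *That the plan makes no link between side effects and background drugs.* It does so operationally: Proposed Dose adjusts background drugs in symptomatic patients, Pharmacologic Interventions documents changes, and the adverse-event definition includes use with another drug. What is missing is an analysis.
- *That excluding phosphodiesterase-5 inhibitors is an error, or that the protocol claims to test the combination.* Background does list the combination among its concerns and then says "These concerns will all be key points of the investigation into a new use of ISDN in Fontan circulations", but the sentence raising it also calls it a contraindication to participation. This is loose wording. Patients on other regimens remain eligible, so the trial is not silent on polypharmacy altogether.
- *That a low count will be declared a success.* No success criterion is set for objective 2.

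**Conclusion.** The point holds as a mismatch between an objective and its analysis. The plan yields neither a patient-level side-effect rate with an interval nor any analysis by background drug, and the objective's scope is wider than the eligible population. In the most favourable result, 0 of 15, rates up to 21.8% (two-sided) or 18.1% (one-sided) remain compatible with the data. A true rate of exactly 20% is therefore excluded by the one-sided limit but not by the two-sided one, and the plan does not say which applies. With one or two patients affected, the two-sided limits are 31.9% and 40.5%.

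These figures assume that all 15 contribute. The plan gives no dropout rate; if only 12 did, zero events would leave 1 − 0.025^(1/12) = 26.5%. No VO2 estimate and no safety procedure is affected. This is a low-cost improvement to what the trial may claim.

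**What to change.** 1. **Secondary Objectives, item 2.** Reword along these lines: *to estimate the proportion of patients with ISDN side effects among Fontan patients not taking phosphodiesterase-5 inhibitors or organic nitrates*.
2. **Statistical Analyses.** Beside the event counts, report the number and proportion of patients with each side effect, with an exact (Clopper-Pearson) two-sided 95% confidence interval. Naming the method covers every possible result.
3. **Statistical Analyses.** List each affected patient against the background drugs in use at the time of the event, taken from the Visit 1 review plus the changes documented under Pharmacologic Interventions. Keep this descriptive; 15 patients do not support comparisons between drug groups.
4. **Study Endpoints.** Add side-effect incidence, to match Study Design.
5. **Background (optional).** Make clear that the phosphodiesterase-inhibitor combination is outside what the trial investigates.

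The cost is one extra descriptive table from data the plan already collects, and a safety statement less favourable than the present objective implies. No patients, visits or clinical procedures are added.
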